### Notes:

- o The 2 samples need to be obtained 2 to 16 weeks apart.
- One sample can be obtained from the patient's medical history and 1 sample can be obtained during the screening period, or both samples can be obtained during the screening period.
- O A third sample may be collected if the variability between the first 2 samples exceeds the limits in Inclusion Criterion 8b and one of these values is deemed spurious.
- 9. Has no other cause of chronic liver disease (eg, autoimmune disorder, alcoholic liver disease, drug-induced liver disease, primary biliary cholangitis, primary sclerosing cholangitis, hepatitis B virus, hepatitis C virus [HCV], Wilson's disease, α-1-antitrypsin deficiency, hemochromatosis) and has not had a liver transplant.
- 10. If the patient has type 2 diabetes mellitus (T2DM), he/she has stable T2DM, defined as hemoglobin A1c (HbA1c) ≤9.5% at screening and no new symptoms associated with decompensated diabetes in the previous 3 months.
- 11. Has a stable body weight, defined by no more than a 5% loss in initial body weight for at least 3 months or since the liver biopsy was performed, whichever is longer.
- 12. Has a BMI  $\geq$ 25 kg/m^2 and  $\leq$ 50 kg/m^2.
- 13. Is willing to undergo a liver biopsy after 52 weeks of treatment.
- 14. Is not of childbearing potential or, if of childbearing potential, is not pregnant as confirmed by a negative serum human chorionic gonadotropin (hCG) test at screening and is not planning a pregnancy during the course of the study.

Note: A woman is considered of childbearing potential following menarche and until becoming postmenopausal unless permanently sterile (permanent sterilization methods include hysterectomy, bilateral salpingectomy, and bilateral oophorectomy). A postmenopausal state is defined as no menses for  $\ge 12$  consecutive months without an alternative medical cause. A follicle-stimulating hormone (FSH) level in the postmenopausal range will be used to confirm a postmenopausal state in women  $\le 55$  years of age.

- 15. Male and female patients of childbearing potential must agree to use a dual method of contraception (a highly effective method of contraception in conjunction with a barrier contraception) consistently and correctly from the first dose of study drug until 90 days after the last dose of study drug. Highly effective methods of contraception are those that result in a failure rate of less than 1% per year when used consistently and correctly and include the following: hormonal intrauterine devices; hormonal contraceptives (oral birth control pills, depo, patch, or injectable); male sterilization performed more than 6 months prior to screening; and complete abstinence from sexual intercourse (if this is the patient's usual and preferred lifestyle). Barrier methods of contraception include male or female condoms used in combination with a separate spermicide product (eg, foam, gel, film, cream, or suppository).
- 16. Male patients must agree to abstain from sperm donation from the first dose of study drug until 90 days after the last dose of study drug.

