### Notes:

- The 2 samples need to be obtained 2 to 16 weeks apart.
- One sample can be obtained from the patient's medical history and 1 sample can be obtained during the screening period, or both samples can be obtained during the screening period.

- o A third sample may be collected if the variability between the first 2 samples exceeds the limits in Inclusion Criterion 8b and one of these values is deemed spurious.
- 9. Has no other cause of chronic liver disease (eg, autoimmune disorder, alcoholic liver disease, drug-induced liver disease, primary biliary cholangitis, primary sclerosing cholangitis, hepatitis B virus, hepatitis C virus [HCV], Wilson's disease, α-1-antitrypsin deficiency, hemochromatosis) and has not had a liver transplant.
- 10. If the patient has type 2 diabetes mellitus (T2DM), he/she has stable T2DM, defined as hemoglobin A1c ≤9.5% at screening and no new symptoms associated with decompensated diabetes in the previous 3 months.
- 11. Has a stable body weight, defined by no more than a 5% loss in initial body weight for at least 3 months or since the liver biopsy was performed, whichever is longer.
- 12. Has a body mass index  $\ge 25 \text{ kg/m}^2$  and  $\le 50 \text{ kg/m}^2$ .
- 13. Is willing to undergo a liver biopsy after 52 weeks of treatment.
- 14. Is not of childbearing potential or, if of childbearing potential, is not pregnant as confirmed by a negative serum human chorionic gonadotropin test at screening and is not planning a pregnancy during the course of the study.
  - Note: A woman is considered of childbearing potential following menarche and until becoming postmenopausal unless permanently sterile (permanent sterilization methods include hysterectomy, bilateral salpingectomy, and bilateral oophorectomy). A postmenopausal state is defined as no menses for  $\ge 12$  consecutive months without an alternative medical cause. A follicle-stimulating hormone level in the postmenopausal range will be used to confirm a postmenopausal state in women  $\le 55$  years of age.

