# 6.3.1 Visit 2 (Week 0)

The following procedures will be performed at Visit 2 (Week 0):

- Reassess inclusion/exclusion criteria prior to dosing to ensure no changes in eligibility have occurred since screening.
- Obtain medical history.
- Record concomitant medications.
- Measure body weight and calculate BMI (using height at screening).
- Calculate iron-corrected T1 values using screening MRI.
- Perform complete physical examination.
- Collect vital signs (blood pressure [3 readings], pulse rate, and body temperature) with the patient in the sitting position after 5 minutes of rest and before any blood draws.

- Collect fasting blood sample for the following:
  - o Hematology, biochemistry, coagulation, and lipid panels.
  - o Lipoprotein particle size.
  - o Serum pregnancy test (only for women of childbearing potential).
  - o Biomarkers (HOMA-IR, hsCRP, Pro-C3, and ELF panel).
  - o Lipidomic analyses (in a subgroup of patients, even if using existing samples).
- Collect urine sample for urinalysis.
- Perform 12-lead ECG after the patient has been resting in the supine position for at least 10 minutes.
- Randomize eligible patients prior to dosing.
- Assess adverse events.
- Collect a predose PK blood sample.

Note: For those patients participating in the intensive PK subset, collect PK blood samples in relation to the first dose of study drug at the following timepoints: predose (within 1 hour prior to the first dose), followed by 1, 2, 3, 4, 6, and 8 hours postdose ( $\pm 10$  minutes) at Visit 2 (Day 0) and 24 hours postdose ( $\pm 1$  hour, but prior to the second dose of study drug on Day 1).

- Administer first dose of study drug on site.
- Dispense study drug and provide dosing instructions for off-site dosing until next study visit.

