# 8.4 Pregnancy Reporting

If a patient becomes pregnant during the study or within the safety follow-up period (ie, prior to the Safety Follow-up Visit), the Investigator is to stop dosing with study drug(s) immediately, and the patient should be withdrawn from the study. Early termination procedures should be implemented at that time.

A pregnancy is not considered to be an adverse event or SAE; however, it must be reported to Medpace Clinical Safety within 24 hours of knowledge of the event. Medpace Clinical Safety will then provide the Investigator/site the Exposure In Utero (EIU) form for completion. The Investigator/site must complete the EIU form and fax/email it back to Medpace Clinical Safety.

If the female partner of a male patient becomes pregnant while the patient is receiving study drug or within the safety follow-up period, the Investigator should notify Medpace Clinical Safety as described above.

The pregnancy should be followed until the outcome of the pregnancy, whenever possible. Once the outcome of the pregnancy is known, the EIU form should be completed and faxed/emailed to Medpace Clinical Safety. If the outcome of the pregnancy meets the criteria for immediate classification as an SAE (ie, postpartum complication, spontaneous abortion, stillbirth, neonatal death, or congenital anomaly), the Investigator should follow the procedures for reporting an SAE.

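### At Visit 2 the only pregnancy test is a serum hCG drawn on the day of randomisation and first dose, and no supplied text requires a negative result first

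*Protocol*

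**What the plan says.** **Eligibility.** For a woman who could conceive, inclusion criterion 14 requires that she "is not pregnant as confirmed by a negative serum human chorionic gonadotropin (hCG) test at screening". It also asks that she have no plans to conceive while on study. The Synopsis has the same wording. Section 4.2 contains no separate pregnancy exclusion. Inclusion 15 requires dual contraception from the first dose until 90 days after the last.

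**Visit 2 (Section 6.3.1).** The site is told to "Reassess inclusion/exclusion criteria prior to dosing to ensure no changes in eligibility have occurred since screening". The same visit includes a serum pregnancy test, listed with the other fasting bloods, and the instructions "Collect urine sample for urinalysis", "Randomize eligible patients prior to dosing" and "Administer first dose of study drug on site". Drug is then dispensed to last until the next visit.

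**Test schedule.** Section 8.7, Appendix A footnote l and Appendix B (Endocrinology, note 1) agree: serum hCG at screening, Week 0 and study exit, and urine hCG at every other visit. A positive urine test is confirmed by serum. The first urine hCG therefore falls at Week 4.

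**Once pregnancy is known.** Section 8.4 says "the Investigator is to stop dosing with study drug(s) immediately" and has the patient withdrawn. Section 4.3 also lists pregnancy as a reason for withdrawal.

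**The concern.** A pregnancy test on the day of first dosing protects the patient only if its result can stop the dose. Here the blood is drawn, the patient is randomised and the capsules are given at one visit, and nothing supplied links the result to either later step. If it comes back after the visit, the only result available at dosing is the screening one, which may be weeks old.

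The protocol treats fetal exposure as worth preventing: it demands dual contraception, tests at every visit and withdraws a pregnant patient. Yet no contraception is mandated between the screening test and Visit 2, which is when that test goes out of date. What is at stake is avoidable early exposure of a rare pregnancy. Power, type I error and the primary estimate are not affected.

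**Working it through.** The protocol gives no figure to reproduce. The check compares the relevant texts and works out the age of the screening test.

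**1. Age of the screening test at first dose.** The Study Day row of Appendix A puts screening at Day -56 to Day -1 and Visit 2 at Day 0 with a ±0-day window. The test is therefore 1 to 56 days old (8 weeks × 7 = 56). Appendix G lets screening run to 12 weeks where COVID-19 affects conduct: 12 × 7 = 84 days. Appendix G then requires the screening MRI-PDFF to be within 8 weeks of randomisation, but sets no such limit for hCG. The distribution of ages within these ranges is not given.

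**2. Is a Week 0 result required before dosing?**

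| Place | What it fixes | Result needed first? |
|---|---|---|
| Inclusion 14 (Synopsis, 4.1) | Negative serum test at screening | Screening result only |
| 3.1 | Visit 2 baseline assessments collected before dosing | Timing of collection, not of the result |
| 6.3.1 | Serum test, randomisation and first dose at one visit | Not stated |
| 8.7; Appendix A footnote l; Appendix B | Which test at which visit | Not stated |
| Appendix A footnote c | General eligibility re-check before dosing | Week 0 hCG not named |
| 8.4 | Stop and withdraw | Applies after pregnancy is known |

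**3. Can the re-check be completed with the Week 0 result pending?** It covers all criteria and cites none by number. Its purpose reaches a new pregnancy. But a site working through the criteria as written finds criterion 14 met by the screening result. Other criteria are timed differently: the transaminase limits in inclusion 7 and the laboratory exclusions in exclusion 10 apply on entry into the study. So yes, the re-check can be completed on the written words with the only current test outstanding.

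**4. Is a late result plausible?** Turnaround is not stated. Section 8.7 leaves sample handling and methods to the Laboratory Manual, which was not supplied. The serum hCG is listed with the laboratory panels, and Appendix G prefers the central laboratory for study-specific tests. A result after the visit is plausible but not shown.

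**5. Exposure if it is late.** Doses taken equal the morning doses that fall before the result: none if it is back before the first dose, one if it is back before the second. The documents do not say which applies.

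**6. Who could still benefit.** This protocol version already reports the interim analysis. Its Table 2 shows 46 + 46 + 47 = 139 patients in the treatment arms, so at most about 264 - 139 = 125 of the planned patients remained to be randomised. The share who are women of childbearing potential is not given.

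**The case against.** The best defence is that the protocol already covers this in substance. The core of criterion 14 is that the woman is not pregnant, and the screening test is the means of confirmation. A re-check for changes since screening naturally includes a new pregnancy, and Section 6.3.1 lists the serum test ahead of randomisation and dosing. On that view only a clarifying sentence is missing, and it may already be in the Laboratory Manual. Section 8.4, the withdrawal rule and the Week 4 urine test are backstops. The supplied documents contain no reproductive-toxicity data from which to judge the harm of a few doses.

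Much of this stands. The intent is clear, the backstops are real, and a same-day result would leave no exposure. What it does not answer is that an eligibility safeguard should not depend on reading intent into a criterion whose wording is met by an old test. Nor should it depend on a manual that protocol readers may not have. Section 8.4 shortens an exposure; it cannot prevent the first dose.

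A reader might infer that pregnant women will in fact be dosed, that the re-check disregards pregnancy, or that the number exposed can be estimated. The documents support none of these. The first depends on an unknown turnaround, the second contradicts the stated purpose of the re-check, and the third needs a childbearing share and a conception rate that neither document gives.

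**Conclusion.** The point holds as a gap in a patient-safety safeguard. Visit 2 has a serum-only hCG on the day of randomisation and first dose, with no stated requirement that the result be known and negative. As written, the re-check can be satisfied by a test up to 56 days old, or 84 under Appendix G.

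Whether any woman is dosed before her result depends on a turnaround that is not stated and a Laboratory Manual that was not supplied. The number of affected patients cannot be sized from the documents. It would be small: it needs a conception during screening and a late result, and Section 8.4 ends dosing once pregnancy is known. There is no effect on the statistical analysis. The change is worth making because it costs almost nothing.

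**What to change.** - In Section 6.3.1, Section 8.7, Appendix A footnote l and Appendix B, add a urine hCG at Visit 2 for women of childbearing potential, using the urine already collected, and require a negative result before randomisation and the first dose.
- Keep the Week 0 serum test as confirmation. Section 8.7 already has serum confirm a positive urine result at other visits.
- Reword inclusion 14 in the Synopsis and Section 4.1 so that the test must be negative at screening and again before randomisation.
- If the Laboratory Manual already holds such a rule, state it in Section 6.3.1.

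The cost is the rewording, one urine test per woman of childbearing potential still to be randomised, and a short wait at Visit 2. Very recent conceptions would still be missed, since no hCG test detects them; the later tests and Section 8.4 remain the protection there. Endpoints, blinding and analysis are unchanged.

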### 4.2 Exclusion Criteria

A patient who meets any of the following criteria will be excluded from participation in the study:

- 1. Has a known history of alcohol abuse or daily heavy alcohol consumption (females: more than 14 units of alcohol per week; males: more than 21 units of alcohol per week [1 unit of alcohol is equivalent to a half pint of beer {285 mL}, 1 measure of spirits {25 mL}, or 1 glass of wine {125 mL}]). Alcohol abuse will be defined as having an Alcohol Use Disorders Identification Test-Concise (AUDIT-C) score of ≥3 points for men and women AND a full Alcohol Use Disorders Identification Test (AUDIT) score of ≥8 points at screening.
  - Note: Only patients with AUDIT-C scores  $\geq 3$  points at screening will receive the full AUDIT and will be excluded if they score  $\geq 8$  points on the full AUDIT. Patients with AUDIT-C scores  $\leq 3$  points will not receive the full AUDIT.
- 2. Has had bariatric surgery within the past 5 years or has bariatric surgery planned to occur during the study.
- 3. Has significant systemic or major illnesses other than liver disease, including pulmonary disease, renal failure, organ transplantation, serious psychiatric disease, or malignancy that, in the opinion of the Investigator, would preclude treatment with NST-4016 or confound the study results. This would include any malignancy under evaluation, or diagnosed and/or treated within the past 2 years except for squamous or non-invasive basal skin cell or cervical carcinoma in-situ.
- 4. Has a recent (within 6 months) history of cardiac dysrhythmias and/or cardiovascular disease, including congestive heart failure (class C and D of the American Heart Association [AHA]), unstable coronary artery disease, cerebrovascular disease, or myocardial infarction.
- 5. Has uncontrolled arterial hypertension.
- 6. Has hepatitis B surface antigen >0, HCV antibody and HCV polymerase chain reaction (PCR) >0 (HCV PCR only required for patients who test positive for HCV antibody; patients with a confirmed history of HCV infection can be included if HCV PCR has been negative for at least the last 2 years), or human immunodeficiency virus (HIV) infection.
- 7. Has type 1 diabetes mellitus.
- 8. Has diabetic ketoacidosis.

- 9. Has a history of liver decompensation, such as ascites, esophageal varices, and hepatic encephalopathy.
- 10. Has any of the following exclusionary laboratory results upon entry into the study:
  - a. Hemoglobin  $\leq 11$  g/dL for females and  $\leq 12$  g/dL for males.
  - b. White blood cell count  $\leq 2.5 \text{ K/}\mu\text{L}$ .
  - c. Neutrophil count  $\leq 1.5 \text{ K/}\mu\text{L}$ .
  - d. Platelet count  $\leq 150 \text{ K/}\mu\text{L}$ .
  - e. Total bilirubin  $\ge 1.3$  mg/dL. Patients with total bilirubin  $\ge 1.3$  mg/dL can be included if direct bilirubin is within normal ranges in the setting of Gilbert's syndrome.
  - f. Albumin < 3.6 g/L.
  - g. International Normalized Ratio ≥1.3, unless due to anti-coagulant therapy.
  - h. Thyroid-stimulating hormone  $> 1.5 \times ULN$ .
  - i. Estimated glomerular filtration rate (eGFR) <60 mL/min/1.73 m^2.
  - j. Fasting triglyceride level >300 mg/dL.

Note: Repeat testing may be performed in consultation with the Medical Monitor if any of the above laboratory parameters are outside the specified ranges.

- 11. Has a hemostasis disorder.
- 12. Has any contraindication to liver biopsy or MRI.
- 13. Has any clinically significant ECG abnormality at screening.
- 14. Has participated in any other investigational drug study within the previous 3 months or 5 half-lives of the last dose of the investigational drug, whichever is longer.
- 15. Has a known hypersensitivity to any of the ingredients or excipients of the study drug.
- 16. Has used any drug known to produce hepatic steatosis, including systemic corticosteroids, methotrexate, tetracycline, amiodarone, tamoxifen, estrogens at doses greater than those used for hormone replacement, anabolic steroids, or valproic acid, for more than 2 weeks in the 6 months prior to screening. Local corticosteroid injection for musculoskeletal disorders is permitted, including epidural corticosteroid administration.
- 17. Is unable to comply with the following concomitant medication restrictions:
  - a. Lipid-lowering therapies must be stable for ≥3 months at screening. Fish oil and other omega-3 compounds must also be stable for ≥3 months at screening if the dose is ≥1000 mg per day.
  - b. Antidiabetic drugs, including insulin regimens, must be stable for ≥3 months at screening, with the exception of sodium-glucose cotransporter-2 (SGLT2) inhibitors, and glucagon-like peptide-1 (GLP-1) agonists, which must be stable for ≥6 months at screening.

- c. No vitamin E >400 U/d, pioglitazone, obeticholic acid, or antiobesity drugs for 3 months prior to screening or since the liver biopsy, whichever is longer.
- 18. Has any other condition that, in the opinion of the Investigator, would impede competence or compliance or possibly hinder completion of the study.
- 19. Uses any prohibited medications (see Section 5.6) or any concomitant medications used to treat an exclusionary medical condition.

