  - a. Hemoglobin  $\leq 11$  g/dL for females and  $\leq 12$  g/dL for males.
  - b. White blood cell count  $\leq 2.5 \text{ K/}\mu\text{L}$ .
  - c. Neutrophil count  $\leq 1.5 \text{ K/}\mu\text{L}$ .
  - d. Platelet count ≤150 K/µL.
  - e. Total bilirubin ≥1.3 mg/dL. Patients with total bilirubin ≥1.3 mg/dL can be included if direct bilirubin is within normal ranges in the setting of Gilbert's syndrome.

- f. Albumin  $\leq$  3.6 g/L.
- g. International Normalized Ratio ≥1.3, unless due to anti-coagulant therapy.
- h. Thyroid-stimulating hormone  $> 1.5 \times ULN$ .
- i. Estimated glomerular filtration rate <60 mL/min/1.73 m^2.
- j. Fasting triglyceride level >300 mg/dL.

Note: Repeat testing may be performed in consultation with the Medical Monitor if any of the above laboratory parameters are outside the specified ranges.

- 11. Has a hemostasis disorder.
- 12. Has any contraindication to liver biopsy or MRI.
- 13. Has any clinically significant electrocardiogram (ECG) abnormality at screening.
- 14. Has participated in any other investigational drug study within the previous 3 months or 5 half-lives of the last dose of the investigational drug, whichever is longer.
- 15. Has a known hypersensitivity to any of the ingredients or excipients of the study drug.
- 16. Has used any drug known to produce hepatic steatosis, including systemic corticosteroids, methotrexate, tetracycline, amiodarone, tamoxifen, estrogens at doses greater than those used for hormone replacement, anabolic steroids, or valproic acid, for more than 2 weeks in the 6 months prior to screening. Local corticosteroid injection for musculoskeletal disorders is permitted, including epidural corticosteroid administration.
- 17. Is unable to comply with the following concomitant medication restrictions:
  - a. Lipid-lowering therapies must be stable for  $\geq 3$  months at screening. Fish oil and other omega-3 compounds must also be stable for  $\geq 3$  months at screening if the dose is  $\geq 1000$  mg per day.
  - b. Antidiabetic drugs, including insulin regimens, must be stable for ≥3 months at screening, with the exception of sodium-glucose cotransporter-2 inhibitors, and glucagon-like peptide-1 agonists, which must be stable for ≥6 months at screening.
  - c. No vitamin E >400 U/d, pioglitazone, obeticholic acid, or antiobesity drugs for 3 months prior to screening or since the liver biopsy, whichever is longer.

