## APPENDIX B: CLINICAL LABORATORY ANALYTES

**Biochemistry Panel** 

Alanine aminotransferase Albumin
Alkaline phosphatase Amylase
Aspartate aminotransferase Bicarbonate
Blood urea nitrogen Calcium

Chloride Creatine kinase

Creatinine Estimated glomerular filtration rate

Gamma glutamyl transferase Glucose

Inorganic phosphorus Lactate dehydrogenase

Lipase Potassium

Sodium Total bilirubin [1]

Total protein Uric acid

1. If total bilirubin is above the upper limit of normal, add conjugated (direct) bilirubin.

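### Exclusion criterion 10f prints the albumin limit as 3.6 g/L in both places, out of line with the per-decilitre units around it; read literally, the limit excludes effectively nobody.

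*Protocol*

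**What the plan says.** Exclusion criterion 10 lists laboratory results that bar entry. In Protocol Section 4.2, item 10f reads "Albumin < 3.6 g/L". The synopsis copy of the same item reads "Albumin $\leq$ 3.6 g/L". The number and the unit agree in the two copies.

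The other mass-concentration limits in the list are per decilitre. Haemoglobin (10a) is in g/dL, as in "g/dL for females and". Total bilirubin (10e) and fasting triglycerides (10j) are in mg/dL. Albumin is the only one per litre.

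The list closes with a note: "Repeat testing may be performed in consultation with the Medical Monitor if any of the above laboratory parameters are outside the specified ranges". The printed ranges therefore decide both who is excluded and who may be retested. Protocol Section 6.3.1 has eligibility reassessed before dosing at Visit 2.

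Neither document offers a second albumin limit, unit or reference range to settle the matter. Appendix B names albumin only as an analyte ("Alanine aminotransferase Albumin"), and the SAP does not restate the criterion.

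**The concern.** The printed unit makes the limit ten times lower than the same number would be on the per-decilitre scale used by its neighbours. If that puts it far below any value a screened outpatient could have, one of the ten laboratory exclusions (10a to 10j) does nothing as written.

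Two things depend on it. First, whether a patient with low albumin was eligible turns on a unit that the protocol may have misprinted. Second, the question survives the end of enrolment. SAP Section 3.3.1 calls for a listing of inclusion and exclusion violations. SAP Section 3.2.4 removes from the Per-Protocol Population patients whose violations could affect the primary endpoint. Whether a given albumin result counts as a violation depends on which unit was applied.

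**Working it through.** The plan has no calculated figure for this criterion, so there is none to reproduce. The check is a unit conversion followed by a tail calculation under a stated assumption.

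**Step 1: unit conversion.** 1 dL is one tenth of a litre, so g/L ÷ 10 = g/dL.

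- As printed: 3.6 g/L ÷ 10 = 0.36 g/dL.
- The same number read on the list's per-decilitre scale: 3.6 g/dL × 10 = 36 g/L.
- Ratio: 36 ÷ 3.6 = 10.

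**Step 2: distance of the printed limit from plausible values.** The documents give no albumin distribution. Assumption, not from the documents: values are roughly normal, with an outpatient mean of 38 to 45 g/L and a standard deviation (SD) of 2.5 to 4 g/L. The distance in SDs is (mean − 3.6) ÷ SD.

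- Closest case: (38 − 3.6) ÷ 4 = 8.6 SD.
- Farthest case: (45 − 3.6) ÷ 2.5 = 16.6 SD.

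The share of patients below 3.6 g/L is zero to the precision computed in all nine combinations tried. A different plausible mean or SD would not change this.

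**Step 3: what the unit decides.** For scale only, and not as a statement of the intended limit, this is the share below 36 g/L under the same assumptions:

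| Assumed mean (g/L) | SD 2.5 | SD 3 | SD 4 |
|---|---|---|---|
| 38 | 21.2% | 25.2% | 30.9% |
| 42 | 0.8% | 2.3% | 6.7% |
| 45 | 0.0% | 0.1% | 1.2% |

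One reading excludes nobody. The other excludes somewhere between almost nobody and about 31%, depending on the population.

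**Step 4: reach into the main analysis.** Albumin does not enter the sample size. The stated design (40% versus 18%, 80% power, 25% dropout) needs 66 per group by the usual two-proportion formula without continuity correction, and 66 ÷ (1 − 0.25) = 88, which matches the protocol. Albumin is also not part of the primary endpoint or of the Cochran-Mantel-Haenszel test.

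**The case against.** The best case on the other side is that this is a misprint with little consequence. Much of that stands.

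- **Other screens remain.** A reader might infer that the trial has no working guard against impaired liver function. The documents do not support that. Inclusion criteria 3 and 5 require histology without cirrhosis, staged F1 to F3 by the central pathology reader. Exclusion 9 bars a history of decompensation. Limits on platelets, bilirubin and INR stand in the same list, and exclusions 11, 12 and 18 add hemostasis disorder, contraindication to biopsy and investigator judgement. The protocol also does not state what the albumin limit is for.
- **Sites may have used a sensible unit.** A reader might infer that sites had to guess. Nothing shows this. Appendix G treats the central laboratory as the default, and Section 8.7 leaves technical laboratory details to a Laboratory Manual that is not among the documents reviewed. By the same token, nothing shows which limit was applied.
- **The operator.** The synopsis prints "Albumin $\leq$ 3.6 g/L" and Section 4.2 prints "Albumin < 3.6 g/L". A reader might call this a second contradiction. It is not asserted here. Comparison signs vary elsewhere in the extracted text: the AUDIT-C note is below 3 in the synopsis and at or below 3 in Section 4.2, and one discontinuation threshold in Appendix E differs between its box and its text. A PDF-reading fault is therefore plausible. The difference also has no practical effect at 3.6 g/L, because no patient would be near that value.
- **Outside knowledge.** The claim that nobody is excluded relies on the general scale of serum albumin, which the documents do not give. The assumption is stated above and the result does not depend on its details. The unit inconsistency within the list needs no outside knowledge.
- **Timing.** The SAP, dated 14 February 2023, describes accrual in the past tense, so a prospective screening check may have little value left. The listing of violations and the Per-Protocol decisions keep the point live.

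None of this repairs the text. The g/L unit appears in both copies, which makes an extraction fault unlikely for the unit itself.

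**Conclusion.** The albumin limit in exclusion 10f is inconsistent with the units of its own list and inoperative as printed. The discrepancy is tenfold, and effectively 0% of patients would meet the literal limit for any assumed mean of 38 to 45 g/L and SD of 2.5 to 4 g/L. The inconsistency itself is read directly from the protocol; only the 0% rests on the assumption.

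This is an error in an operative eligibility threshold. Its effect is confined to who counts as eligible on albumin, and through that to the violation listing and possibly the Per-Protocol Population. It does not affect the primary test or the sample size, and it does not show that any unsuitable patient was enrolled. Which limit was intended is for the sponsor to state.

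**What to change.** 1. Reconcile 10f with the unit convention of the list and the central laboratory's reporting unit, and print the corrected item identically in the synopsis and Section 4.2.
2. Check the comparison sign in both places against the source PDF at the same time, so that one operator is used.
3. Confirm and document which albumin limit was actually applied at screening, and that it was the intended one.
4. Confirm that the same limit is used for the eligibility-violation listing (SAP Section 3.3.1) and for Per-Protocol exclusions (SAP Section 3.2.4). Section 3.2.4 requires the latter to be final before unblinding.

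The cost is a one-line clarification and a check of the screening rule against the recorded data. It needs no extra patients and no change to the primary analysis.
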